9.2 Extent of Exposure

Only subjects enrolled in this study may be treated with ¹²⁴I-AT-01. During the study, qualified clinical site staff will administer all study drug. The date and time for each dose will be recorded in the CRFs.

The actual dose of ¹²⁴I-AT-01 will be summarized in mCi and mg by study visit. The administration type (infusion, IV bolus), duration of administration (for infusions) and number of subjects experiencing an administration interruption and associated reason for interruption will be summarized by study visit.

 124 AT-01 compliance is defined as receiving 1 mCi (+/- 10%) (<= 2mg 124 AT-01). KI compliance is defined as receiving KI orally for 3 days in the specified time periods. The number of and percent of compliant subjects for 124 AT-01 and for KI will be summarized by visit.

A listing of all administrations of ¹²⁴I-AT-01 will be provided by subject and visit.

A listing of all administrations of potassium iodide (KI) will be provided by subject and visit.

9.3 Adverse Events

Adverse events will be coded using the Medical Dictionary for Regulatory Activities (MedDRA) Version 24.1 to identify the system organ class and preferred term. All AEs and SAEs will be recorded from the time of informed consent until the final EOS telephone follow-up (~Week 10).

Treatment-emergent AEs are defined as events that are newly reported or reported to worsen in severity after the start of treatment. Adverse events that occur after the treatment start date, occur on the treatment start date with a time that is equal to or after treatment start time, or that have a missing AE start date will be categorized as treatment-emergent. Treatment-emergent AEs will be summarized for the Safety Set.

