4.1.2 Pre-Administration Period

Subjects will begin therapy with KI 130 mg (e.g., iOSAT, Potassium Iodide Oral Solution USP, 65 mg/mL) orally once every day for 3 days beginning at least 30 minutes and within 24 hours prior to dosing with ¹²⁴I-AT-01 on the Day 1 and Week 6 visits to block radioactive iodine uptake in the thyroid gland.

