9.5.4 Safety Analysis

Safety will be assessed through reported adverse events (graded using NCI CTCAE version 5) and changes in laboratory parameters.

Adverse Events

All adverse events occurring during the study will be recorded and classified based on Medical Dictionary for Regulatory Activities (MedDRA) terminology. Only treatment-emergent adverse events (TEAEs), which are adverse events that occur after the start of study drug, will be summarized.

The number and percentage of subjects experiencing TEAEs and SAEs will be tabulated for the safety population by system organ class (SOC) and preferred term (PT). TEAEs and SAEs will be tabulated by severity and relationship to study medication. Each subject will be counted only once within a SOC or a PT by using the AE with the highest severity or greatest relationship, respectively, within each category.

TEAEs or SAEs leading to early discontinuation will be summarized as described above. Treatment-emergent adverse events starting on the day of dosing at each dosing visit will be summarized by SOC and PT to evaluate potential infusion-related reactions.

Listings for all reported adverse events, including SAEs, will be provided. In addition, separate listing for SAEs, AEs leading to premature withdrawal from the study, and all deaths will be generated.

Vital signs will include blood pressure (mmHg) and heart rate (beats per minute). Vital signs will be summarized at Baseline and for each study visit when vital signs were obtained. Changes from Baseline in vital sign measurements will also be summarized. Baseline is defined as the last vital signs obtained prior to the initiation of study drug.

Clinical Laboratory Analyses

Baseline for clinical chemistry parameters is defined as the most recent laboratory measurement obtained prior to the initiation of study drug. Clinical laboratory parameters from the tests itemized in Section 10.2, will be summarized as both absolute value and change from Baseline for each visit per the SoA (Section 1.3).

Laboratory parameters with quantitative abnormalities will be listed as 'flagged' based on the Sponsor's internal guidelines. Flagged laboratory parameters will be presented by incidence and frequency.

Clinical safety laboratory tests performed during the study will be analyzed by a central clinical laboratory.

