5 ANALYSIS SETS

The analysis sets for the planned analyses are defined as follows:

• Enrolled Set

The Enrolled Set is defined as all subjects who signed the informed consent form (ICF) and met eligibility criteria.

• Safety Set

Version Date: 2022-12-16

The Safety Set is defined as all subjects who receive any amount of ¹²⁴I-AT-01. The Safety Set will be used for safety analyses.

• Image Evaluable Set

The Image Evaluable Set (IES) is defined as all subjects who undergo PET/CT scans on both Day 1 and 6 to 8 weeks after Day 1 and who have evaluable images at both time points. The IES will be used for analyses of repeatability.

Version: 2.0

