9.3.2 Subject-level and Event-level Summary of AEs

A summary table will be presented to reflect a count and percentage of subjects experiencing at least 1 TEAE in each system organ class and preferred term and a count of TEAEs occurring in subjects in the Safety Set within each system organ class and preferred term. All percentages will use the number of subjects in the Safety Set as the denominator. A subject

Page 22 of 38

will be counted only once for a category. For the event-level summaries, subjects experiencing more than 1 AE within a category be counted more than once. Tabular summaries will be sorted by descending frequency in subject counts by system organ class and preferred term.

TEAEs and SAEs will also be tabulated by CTCAE grade, relationship to AT-01 administration, and relationship to KI. Each subject will be counted only once within a SOC or PT by using the AE with the highest severity or greatest relationship within each category.

Records with missing CTCAE grade will be counted as severe.

Records with missing relationship to AT-01 or KI will be counted as related.

Listings for all reported adverse events will be provided.

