15 ATTACHMENTS

15.1 Table of Contents for Data Display Specifications

Tables		
Number	Title	Population
14.1.1	Summary of Subject Disposition	All Subjects
14.1.2.1	Summary of Subject Demographics and Baseline Characteristics	Safety
14.1.3.1	Medical History by System Organ Class and Preferred Term	Safety
14.1.3.2	Surgical or Procedural History by System Organ Class and Preferred Term	Safety
14.1.4.1	Summary of Prior Medications by Drug Class and Preferred Term	Safety
14.1.4.2	Summary of Concomitant Medications by Drug Class and Preferred Term	Safety
14.1.4.3	Summary of Prior Medications for the Treatment of Systemic Amyloidosis by Drug Class and Preferred Term	Safety
14.1.4.4	Summary of Concomitant Medications for the Treatment of Systemic Amyloidosis by Drug Class and Preferred Term	Safety
14.1.5	Summary of Protocol Deviations	Enrolled
14.1.6	Summary of Treatment Exposure	Safety
14.2.1.1.1	Within Reader Repeatability Coefficients by Reader, Visit, and SUV Metric by Organ	Image Evaluable Set
14.2.1.1.2	Within Reader Repeatability Coefficients by Reader, Visit, and SUV Metric by Organ and Amyloid Type	Image Evaluable Set

Page 33 of 38

14.2.1.2.1	Between Visit Repeatability Coefficients by Reader and SUV Metric by Organ	Image Evaluable Set
14.2.1.2.2	Between Visit Repeatability Coefficients by Reader and SUV Metric by Organ and Amyloid Type	Image Evaluable Set
14.2.1.3	Summary of Repeatability Analysis Results	Image Evaluable Set
14.2.2.1	Among Reader Intraclass Correlation Coefficients by Visit and SUV Metric by Organ	Image Evaluable Set
14.2.2.2	Among Reader Intraclass Correlation Coefficients by Visit and SUV Metric by Organ and Amyloid Type	Image Evaluable Set
14.2.3.1	Summary of Inter-rater Agreement by Visit by Organ	Image Evaluable Set
14.2.3.2	Summary of Intra-rater Agreement by Expert Radiologist by Organ	Image Evaluable Set
14.2.4	Coefficients of Variation by Visit by Organ	Image Evaluable Set
14.3.1.1	Overall Summary of Treatment-Emergent Adverse Events	Safety
14.3.1.2	Treatment-Emergent Adverse Events by System Organ Class and Preferred Term	Safety
14.3.1.3	Treatment-Emergent Adverse Events by System Organ Class, Preferred Term, and CTCAE Grade	Safety
14.3.1.4.1	Treatment-Emergent Adverse Events by System Organ Class, Preferred Term, and Relationship to AT-01	Safety
14.3.1.4.2	Treatment-Emergent Adverse Events by System Organ Class, Preferred Term, and Relationship to KI	Safety

Page **34** of **38**

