16.2.4.6	Pregnancy Test Results	Safety
16.2.5.1	¹²⁴ I-AT-01 Administration	Safety
16.2.5.2	Potassium Iodide Administration	Safety
16.2.6	Imaging Results	Image Evaluable
16.2.7.1	Adverse Events by Subject, System Organ Class, and Preferred Term	Safety
16.2.7.2	Treatment-Emergent Adverse Events on Day of Dosing by Subject, System Organ Class, and Preferred Term	Safety
16.2.7.3	Treatment-Emergent Adverse Events on Day of Dosing Reported on the AT01 Administration CRF	Safety
16.2.8.1	Laboratory: Chemistry	Safety
16.2.8.2	Laboratory: Hematology	Safety

Page **37** of **38**

Version Date: 2022-12-16 Version: 2.0

Document Control No.: TMP-SA-008-01 Template Effective Date: 23 Mar 2021

Attralus, Inc.

 $Statistical\ Analysis\ Plan-AT01-001$

16.2.8.3	Laboratory: Urine and Biomarker Results	Safety
16.2.8.4	Vital Signs	Safety

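### The table of adverse events by relationship to KI uses a clock and a population tied to the first 124I-AT-01 dose, so first-course KI reactions that begin before that dose are not tabulated

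*SAP*

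**What the plan says.** KI is taken by mouth around each 124I-AT-01 dose, "orally once every day for 3 days beginning at least 30 minutes and within 24 hours prior to dosing" (protocol 4.1.2). The protocol's Schedule of Activities says that subjects take it themselves.

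The SAP undertakes to report KI attribution: "TEAEs and SAEs will also be tabulated by CTCAE grade, relationship to AT-01 administration, and relationship to KI" (9.3.2). The display list (SAP 15.1) carries this as Table 14.3.1.4.2, "Treatment-Emergent Adverse Events by System Organ Class, Preferred Term, and Relationship to KI", in the Safety population.

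Treatment-emergent events are "events that are newly reported or reported to worsen in severity after the start of treatment" (SAP 9.3). Operationally, they start after the treatment start date, or "occur on the treatment start date with a time that is equal to or after treatment start time", or have no start date. Protocol 9.5.4 puts it this way: "Only treatment-emergent adverse events (TEAEs), which are adverse events that occur after the start of study drug, will be summarized".

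On population, SAP 5 states: "The Safety Set is defined as all subjects who receive any amount of" 124I-AT-01. Listing 16.2.7.1, "Adverse Events by Subject, System Organ Class, and Preferred Term", is also labelled Safety. SAP 9.3.2 and protocol 9.5.4 both promise listings of every reported adverse event and state no population. SAP 9.4 promises separate SAE, withdrawal and death listings, which the display list does not name.

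**The concern.** A table of KI-related events should start counting when KI exposure starts. Here KI exposure always starts before the clock does. The excluded interval follows the first dose of the first course, which is when an acute intolerance could first appear.

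The two courses are also treated differently. Before Day 1 dosing, a KI reaction is a pre-treatment event. Before Week 6 dosing, the same reaction is treatment-emergent, because it follows the first 124I-AT-01 dose. The secondary objective is the tolerability of repeat doses, so a counting rule that differs between the visits is unwelcome, even if few events are affected.

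Finally, a subject who reacts to KI and never receives 124I-AT-01 falls outside the Safety Set. Whether that event is displayed anywhere then depends on whether the SAP text or the display list is followed.

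**Working it through.** **Step 1: what starts the clock.** SAP 9.3 does not name the treatment, so the anchor is inferred from these places:

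- Protocol 9.5.4 ties treatment emergence to the start of study drug.
- Protocol 4.1 and SAP 3.3 call 124I-AT-01 the only study intervention.
- SAP 9.1 imputes partial dates, for defining treatment emergence, from 124I-AT-01 administration dates.
- SAP 9.2 says that site staff give all study drug, whereas KI is self-administered.

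Nothing points to KI. The inference is strong, but it is an inference.

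**Step 2: apply the rules to illustrative cases.** Hours are relative to the 124I-AT-01 dose of that visit. Dates and times are complete, and no event worsens later.

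| Case | Safety Set | KI table 14.3.1.4.2 | Day-of-dosing summary | Listing 16.2.7.1 as labelled |
|---|---|---|---|---|
| Day 1: KI at −20 h, onset −18 h, dosed | yes | **no** | no | yes |
| Day 1: KI at −0.6 h, onset −0.2 h, dosed | yes | **no** | **no** | yes |
| Day 1: KI at −0.6 h, onset +1 h, dosed | yes | yes | yes | yes |
| Day 1: KI at −20 h, onset −18 h, never dosed | **no** | **no** | **no** | **no** |
| Week 6: KI at −0.6 h, onset −0.2 h, dosed | yes | yes | **yes** | yes |
| Week 6: onset 10 h before the planned dose, dose withheld | yes | yes | no dose given | yes |

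The second and fifth rows are the same clinical event with different results. The day-of-dosing column follows from SAP 9.4.1, which summarizes treatment-emergent events starting on the dosing day at each dosing visit.

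**Step 3: the never-dosed subject.** The protocol's safety population (protocol 9.4) also requires a PET/CT scan or some 124I-AT-01, so it does not bring this subject in. Disposition covers everyone who signed consent (SAP 6.1) and would show the discontinuation and its reason, but it is not an AE output.

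**Step 4: size.**

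- Planned KI doses per subject, with the 3-day course of protocol 4.1.2: 2 courses × 3 = 6. At 24-hour spacing, one precedes the first 124I-AT-01 dose: 1/6 = 16.7%. (Protocol Table 1 words the course differently, as before and for 3 days after dosing. The two descriptions need reconciling.)
- The uncounted window runs from the first KI dose to the first 124I-AT-01 dose, so it lasts between 0.5 and 24 hours.
- One missed dosed subject out of 20 is 1/20 = 5 percentage points. This does not describe a never-dosed subject, who is not in the Safety Set denominator.
- The documents give no KI reaction rate. For scale, assume a per-subject probability p of a reaction in this window. The chance of at least one among 20 is 1 − (1 − p)^20:

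| Assumed p | Expected number, 20p | Chance of at least one |
|---|---|---|
| 1% | 0.2 | 18.2% |
| 2% | 0.4 | 33.2% |
| 5% | 1.0 | 64.2% |
| 10% | 2.0 | 87.8% |

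**The case against.** The strongest reply is that the clock suits the study. The secondary objective concerns 124I-AT-01, KI tolerability is not an endpoint, and the protocol itself counts from the start of study drug. That holds for the AT-01 tables. It does not justify using the same clock for a table that the SAP chose to build on KI attribution.

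Three stronger readings are tempting, and the documents do not support them.

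- *All reactions to the first KI dose are lost.* Only those that begin before 124I-AT-01 are. Reactions that start or worsen after dosing, or have no start date, count. SAP 9.1 also moves some partial start dates to the administration date. In dosed subjects, pre-dose events remain in Listing 16.2.7.1, which is not limited to treatment-emergent events.
- *Any KI reaction that prevents dosing appears in no AE output.* A Week 6 reaction that blocks the second dose is tabulated and listed. For the first dose, the absence rests on one population label that contradicts the SAP's own text. It is an inconsistency to settle, not an established omission.
- *KI-related incidence will look higher at the repeat visit.* No planned table shows that comparison. Table 14.3.1.4.2 is not split by visit, and the by-visit tables are not split by KI relationship. The visit difference can show only in the day-of-dosing summary, and only for reactions that begin on the dosing day before the dose.

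A practical objection has some force. The documents do not state that clock times are recorded for self-administered KI. However, SAP 9.2 defines KI compliance by intake in specified time periods, which implies that some timing is captured.

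**Conclusion.** The point stands in limited form. As written, the rules leave first-course KI reactions with onset before the first 124I-AT-01 dose out of the one table meant to show KI-related events, and count the same event before the second dose. They also give a same-day pre-dose reaction different treatment at Day 1 and Visit 2 in a summary meant to screen for infusion-related reactions. For a subject stopped before any 124I-AT-01, the text and the display list conflict.

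The likely size is small. Known KI allergy is an exclusion criterion (protocol 5.2), the window is under a day, and the count of one dose in six assumes 24-hour spacing. The probabilities above rest on assumed rates. The conclusion also assumes that treatment start in SAP 9.3 means the first 124I-AT-01 dose; if another start was meant, the section needs to say so. No repeatability result is affected. The change is still worth making before database lock, because it corrects a rule that undercounts by construction.

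**What to change.** In the SAP:

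1. State in 9.3 that treatment start is the first 124I-AT-01 dose for the AT-01 tables.
2. For Table 14.3.1.4.2, count events with onset at or after the first KI dose, in all subjects who took any KI. Retitle the table and give its denominator. If only KI dates are available, say how same-day events are assigned.
3. In the day-of-dosing summary (9.4.1), apply one rule at both visits to events that begin before that visit's dose. Since the display is meant for infusion-related reactions, leaving them out at both visits would fit its purpose.
4. Set Listing 16.2.7.1 and the KI administration listing 16.2.5.2 to All Subjects, a label already used for Listings 16.2.1 and 16.2.3.1. Add the SAE, withdrawal and death listings promised in 9.4 to the display list with the same population.

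The cost is SAP wording, one derived flag and some population labels, with no protocol change. No new data should be needed if KI timing is captured as SAP 9.2 implies; this should be confirmed. KI-related counts may rise slightly, and the KI table's denominator may differ from the Safety Set.

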9.1 Overview of Safety Analysis Methods

The safety analyses will be performed for the Safety Set and will include treatment-emergent adverse events (TEAEs), serious adverse events (SAEs), vital signs, biomarkers, and concomitant medications. Tabular summaries of descriptive statistics will be presented for all subjects included in the Safety Set.

For all safety endpoints, baseline will b

e the last non-missing value before administration of ¹²⁴I-AT-01.

Safety data will not be imputed, except for partial and missing dates, which will be imputed only for defining TEAEs and concomitant medications. Imputed dates will not be presented in data listings.

Partial dates will be imputed for the purposes of defining TEAEs as follows:

- For a missing start day where the month and year are present, the start day will be set to the first day of the month, unless 1) the first day of the month is before the most-recent date of administration of ¹²⁴I-AT-01 and the month and year are the same as the month and year of the most-recent date of administration of ¹²⁴I-AT-01, and 2) the end date is on or after the most-recent date of administration of ¹²⁴I-AT-01or the end date is completely missing, in which case the start day will be set to the most-recent date of administration of ¹²⁴I-AT-01.
- For a missing start day and month where the year is present, the start day and month will be set to January 1st, unless 1) January 1st is before the most-recent date of administration of ¹²⁴I-AT-01 and the year is the same as the year of the most-recent date of administration of ¹²⁴I-AT-01, and 2) the end date is on or after the most-recent date of administration of ¹²⁴I-AT-01 or the end date is completely missing, in which case the start day and month will be set to that of the most-recent date of administration of ¹²⁴I-AT-01.
- For a missing end day where the month and year are present, the end day will be set to the last day of the month, unless the month and year are the same as the month and year of the last contact date for the subject, in which case the end day will be set to that of the subject's last contact date.
- For a missing end day and month where the year is present, the end day and month will be set to the subject's last contact date, unless the year of the subject's last contact date is

Page 21 of 38

greater than the end year, in which case the end day and month will be set to December $31^{\rm st}$.

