9.4.1 TEAEs on Day of Dosing

Infusion-related reactions (IRRs) can be any signs or symptoms experienced by subjects during the infusion of pharmacologic or biologic agents or any event occurring on the first day of the infusion. Treatment-emergent adverse events starting on the day of dosing at each dosing visit will be summarized by SOC and PT in order to evaluate potential IRRs.

A data listing of TEAEs starting on the day of dosing at each dosing visit will be provided.

IRRs which occur during administration will be captured on the AT01 Infusion CRF as any non-blank answer for "If discontinued, provide reason" or "If interrupted, reason for interruption" and will be provided in a listing.

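### Read literally, the SAP's treatment-emergent rule leaves out an adverse event dated on the first dosing day with no start time, while the same untimed event on the second dosing day counts

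*SAP*

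**What the plan says.** SAP 9.3 gives a general definition and then an operational rule. The definition is: "Treatment-emergent AEs are defined as events that are newly reported or reported to worsen in severity after the start of treatment". The rule names three groups:

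1. "Adverse events that occur after the treatment start date";
2. those that "occur on the treatment start date with a time that is equal to or after treatment start time";
3. "or that have a missing AE start date will be categorized as treatment-emergent".

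On incomplete data, SAP 9.1 states: "Safety data will not be imputed, except for partial and missing dates, which will be imputed only for defining TEAEs and concomitant medications". Its rules cover missing days and months. Under stated conditions they move a partial start date to the most recent administration date. No rule covers a missing clock time.

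For potential infusion-related reactions, SAP 9.4.1 states: "Treatment-emergent adverse events starting on the day of dosing at each dosing visit will be summarized by SOC and PT". That table therefore inherits the 9.3 classification. So do the overall, SOC/PT, serious, withdrawal, death and hypersensitivity summaries in SAP 9.3.1, 9.3.2, 9.4 and 9.4.3.

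Protocol 9.5.4 defines treatment-emergent events by onset after the start of study drug and sets no clock-time condition. SAP 2 gives the SAP precedence where the two differ.

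**The concern.** TEAE incidence is the first-named secondary endpoint, and the day-of-dosing table is the planned tool for looking at infusion reactions. The SAP counts any event on the dosing day as a possible reaction. A rule that requires a clock time on the first dosing day but not on the second can make the first dose look better tolerated than the second for reasons of record-keeping alone.

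The rule also runs against the SAP's other defaults, which resolve missing adverse-event data conservatively. A missing start date makes an event treatment-emergent (9.3). A missing grade counts as severe and a missing relationship as related (9.3.2). A missing seriousness flag counts as serious (9.4). An event with no date at all is counted, while one known to fall on the first dosing day but lacking a time is not.

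**Working it through.** The plan gives no figure to reproduce. The check applies the three groups in SAP 9.3, as written, to test events. D1 is the first dosing date and D2 is the Visit 2 dosing date.

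Rule as written: TEAE if (date > D1), or (date = D1 and a time exists and time ≥ dose time), or (start date missing).

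| Test event | Rule as written | In day-of-dosing table |
|---|---|---|
| D1, timed before the dose | not TEAE | no |
| D1, timed at or after the dose | TEAE | yes |
| **D1, no time** | **not TEAE** | **no** |
| Day after D1, no time | TEAE | no |
| **D2, no time** | **TEAE** | **yes** |
| D2, timed before the second dose | TEAE | yes |
| Start date missing | TEAE | no |
| Start date missing, end date before D1 | TEAE | no |

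The third and fifth rows differ only in the dosing visit. The last row is an over-count: the recorded end date shows that the event was over before treatment. SAP 6.4 already makes the equivalent check for medications, where a stop date before the first dose overrides a missing start date.

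**Partial dates.** Take a subject dosed only once, with a start date giving the month of that dose but no day, and an end date after the dose. SAP 9.1 moves the start day to the administration date, which is D1. No time is assigned, so the event falls into the third row. The imputation made in order to define TEAEs then does not achieve its purpose. If the date is instead set to D2, the event is after the treatment start date and counts, so the gap arises only at the first dose.

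**Possible size (illustration only).** The planned sample is up to 20 (SAP 3.3). The per-dose reaction rate p and the share u of first-day events with no time are assumptions; the documents give neither.

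- Expected first-dose reactions counted = 20 × p × (1 − u). Expected second-dose reactions counted = 20 × p.
- Chance of losing at least one first-dose reaction = 1 − (1 − p × u)^20.

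For p = 10%, with 20 × 0.10 = 2.0 expected at each dose:

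| u | Counted at first dose | Counted at second dose | Chance of losing ≥1 |
|---|---|---|---|
| 0% | 2.0 | 2.0 | 0 |
| 10% | 1.8 | 2.0 | 0.18 |
| 25% | 1.5 | 2.0 | 0.40 |
| 50% | 1.0 | 2.0 | 0.64 |
| 100% | 0 | 2.0 | 0.88 |

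Over the same span of u, the chance runs from 0 to 0.64 at p = 5% and from 0 to 0.99 at p = 20%. One subject is 1/20 = 5 percentage points.

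**The case against.** **The SAP is silent rather than excluding.** The general definition in 9.3 could be read to include an untimed first-day event, and the SAP's other defaults suggest that inclusion was intended. This stands. But programmers work from the operational sentence, and that sentence has no place for the event.

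**Times may always be present.** Subjects remain on site for a scan about 5 hours after dosing, staff record events throughout the visit (Protocol 4.1.3.1), and source data are recorded in real time (Protocol 10.1.6). This also stands, and the loss may be zero. The exposed part is onset later that day, after discharge. The Schedule of Activities has no contact between Visit 1 and Visit 2 for subjects who continue. That times would then be missing is conjecture, not something the documents say.

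**Other outputs do not depend on the rule.** Reactions that stop or interrupt administration are listed from the infusion CRF (SAP 9.4.1), interruptions are summarized by visit (SAP 9.2), and all events are listed (SAP 9.3.2). This is correct, so a reader should not infer that first-dose reactions vanish from every infusion-reaction output. The CRF route is narrow, however. At 0.1–1 mCi/mL an undiluted 1 mCi bolus is 1–10 mL, which at 5 seconds per mL takes 5–50 seconds (Protocol Table 2). Infusions under Version 1.1 took 2–5 minutes. Reactions after that appear in the listings, which give no incidence.

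**Worsening is covered.** A reader might infer that the SAP omits events that worsen after dosing. The defining sentence includes "events that are newly reported or reported to worsen in severity after the start of treatment", so this is not a gap in the definition, although the operational sentence could usefully repeat it.

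**Second-dose events are not counted everywhere.** In the by-visit summary of SAP 9.4.2, events on the Visit 2 date fit neither time category. The asymmetry holds for the TEAE and day-of-dosing tables, not for that one.

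**Conclusion.** The gap is real on a literal reading. An adverse event dated on the first dosing day with no time, whether recorded that way or imputed to that date, is not classed as treatment-emergent. The same event on the second dosing day is. The possible effect is an undercount of first-dose events in the TEAE and day-of-dosing tables. Separately, undated events that ended before dosing are over-counted.

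The size cannot be fixed from the documents. It depends on whether event times are collected and complete, which neither document states, and it may be zero. A stronger reading would be that times are probably missing at Visit 1, or that reactions are expected mainly at first exposure. The documents support neither.

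Severity is minor to moderate. The outputs are descriptive, there is no hypothesis, the primary endpoint is untouched, and every event is listed. It still deserves correction before database lock, because a stated classification rule would put known events in the wrong group.

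**What to change.** Replace the operational sentence in SAP 9.3 with:

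> An AE is treatment-emergent if it starts, or worsens in grade, on or after the date of the first administration, unless a recorded time shows that the onset or worsening came before that administration. An AE with a missing start date is treatment-emergent unless its end date is before the first administration.

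State that the same rule applies to dates imputed under SAP 9.1.

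In the table of test events, the untimed D1 event becomes a TEAE and enters the day-of-dosing table. The undated event that ended before D1 stops being one. The other six are unchanged, and a D1 event timed before the dose stays out.

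The cost is two sentences and a few lines of derivation code. A few pre-dose Day 1 events without a time may be counted, which is the conservative direction and matches the SAP's other defaults. The change does not make the visits fully symmetrical: an event on the Visit 2 date timed before the second dose remains a TEAE and stays in the day-of-dosing table.
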